4.2.4 Supplementary Analyses

Two supplementary analyses based on differing strategies of handling ICE (as outlined below) are planned for PFS. Note that the attributes of population, variables, and population level summary will remain the same as the primary estimand. The analysis for the supplementary estimands will be conducted only on the primary endpoint investigator assessed PFS.

- PFS assessed by investigator based on hypothetical strategy for use of any non-protocol anti-cancer therapy (NPT) prior to disease progression: To assess the impact of use of any NPT prior to disease progression, the analysis of investigator assessed PFS will be repeated with the ICE of use of any NPT handled using a hypothetical strategy. According to this strategy, patients who start NPT prior to disease progression will be censored at the time of the last

disease status assessment before the initiation of NPT. If patients start any NPT before starting study treatment, then the data of those patients will be censored at the time of randomization. Approaches to handle other ICE (Discontinuation of study treatment prior to disease progression) and analysis method will be the same as mentioned in Section 4.2.2.

- PFS assessed by investigator based on composite strategy for use of any NPT prior to disease progression: In addition to the above estimand, in this case a supplementary estimand for PFS will be estimated by following the composite strategy. According to composite strategy, use of any NPT prior to disease progression will be considered as a PFS event (progression) at the time of initiation of NPT. If patients start any NPT before starting study treatment then the data of those patients will be censored at the time of randomization. Approaches to handle other ICE (Discontinuation of study treatment prior to disease progression) and analysis method will be the same as mentioned in Section 4.2.2.

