4.1.2 Exclusion Criteria

Patients who meet any of the following criteria will be excluded from study entry:

- Metaplastic breast cancer
- Any history of leptomeningeal disease or carcinomatous meningitis
- Any prior systemic therapy for metastatic breast cancer
- Prior treatment with fulvestrant or any selective estrogen-receptor degrader, with the exception of patients that have received fulvestrant or any selective estrogen-receptor degrader as part of neoadjuvant therapy only and with treatment duration of no longer than 6 months
- Prior treatment with any PI3K, AKT, or mTOR inhibitor, or any agent whose mechanism of action is to inhibit the PI3K-AKT-mTOR pathway
- Appropriate for treatment with cytotoxic chemotherapy at time of entry into the study, as per national or local treatment guidelines (e.g., patients with visceral crisis)
- Type 2 diabetes requiring ongoing systemic treatment at the time of study entry; or any history of Type 1 diabetes
- Inability or unwillingness to swallow pills or receive IM injections
- Malabsorption syndrome or other condition that would interfere with enteral absorption
- Known and untreated, or active CNS metastases (progressing or requiring anticonvulsants or corticosteroids for symptomatic control). Patients with a history of treated CNS metastases are eligible, provided they meet all of the following criteria:
 - Measurable disease outside the CNS
 - No ongoing requirement for corticosteroids as therapy for CNS metastases, with corticosteroids discontinued for ≥ 2 weeks prior to enrollment and no ongoing symptoms attributed to CNS metastases
 - Radiographic demonstration of improvement upon the completion of CNS-directed therapy and no evidence of interim progression between the completion of CNS-directed therapy and the screening radiographic assessments
 - Screening CNS radiographic assessments ≥ 4 weeks since completion of radiotherapy
 - No history of intracranial hemorrhage or spinal cord hemorrhage

- Uncontrolled pleural effusion, pericardial effusion, or ascites requiring recurrent drainage procedures biweekly or more frequently
 - Indwelling pleural or abdominal catheters may be allowed, provided the patient has adequately recovered from the procedure, is hemodynamically stable and symptomatically improved.
- Serious infection requiring IV antibiotics within 7 days prior to Day 1 of Cycle 1

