- Any concurrent ocular or intraocular condition (e.g., cataract or diabetic retinopathy) that, in the opinion of the investigator, would require medical or surgical intervention during the study period to prevent or treat vision loss that might result from that condition
- Active inflammatory (e.g., uveitis or vitritis) or infectious (e.g., conjunctivitis, keratitis, scleritis, or endophthalmitis) conditions in either eye or history of idiopathic or autoimmune-associated uveitis in either eye
- Requirement for daily supplemental oxygen
- Symptomatic active lung disease, including pneumonitis
- History of or active inflammatory bowel disease (e.g., Crohn's disease or ulcerative colitis)
 - Patients currently receiving immunosuppressants for inflammatory bowel disease (e.g., sulfasalazines) are considered to have active disease and are *thus* ineligible.
- Any active bowel inflammation (including diverticulitis)
- Symptomatic hypercalcemia requiring continued use of bisphosphonate or denosumab therapy
 - Bisphosphonate and denosumab therapy for bone metastases or osteopenia/osteoporosis is allowed.
- Clinically significant and active liver disease, including severe liver impairment (Child-Pugh Class B/C), viral or other hepatitis, current alcohol abuse, or cirrhosis
- Known HIV infection
 - Sites should include an HIV test during screening, as allowed per local regulations.
- Current severe, uncontrolled systemic disease (e.g., clinically significant cardiovascular, pulmonary, metabolic, or infectious disease) or any other diseases, active or uncontrolled pulmonary dysfunction, metabolic dysfunction, physical examination finding, or clinical laboratory finding giving reasonable suspicion of a disease or condition that contraindicates the use of an investigational drug, that may affect the interpretation of the results, or that renders the patient at high risk from treatment complications
- Chemotherapy, radiotherapy, or any other anti-cancer therapy within 2 weeks before randomization

- Investigational drug(s) within 4 weeks before randomization
- Prior radiotherapy to $\geq 25\%$ of bone marrow, or hematopoietic stem cell or bone marrow transplantation
- Unresolved toxicity from prior therapy, except for hot flashes, alopecia, and Grade ≤ 2 peripheral neuropathy

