At screening, a CT or MRI scan of the brain is required to confirm no progression in patients with previously treated brain lesions; the scan must be within the screening window and ≥ 4 weeks after the completion of radiotherapy. For all other patients, brain scans should be acquired if clinically indicated. At subsequent tumor assessment timepoints, brain scans should be acquired if disease was present at baseline or if clinically indicated.

A documented standard-of-care tumor assessment performed within 28 days prior to Cycle 1, Day 1 may be used for the screening assessment provided it meets the above requirements. Tumor assessments should be performed on schedule (approximately every 8 weeks [± 7 days] for the first 2 years after randomization, and every 12 weeks [± 7 days] thereafter) as described in [Appendix 1](#), regardless of dose delay or early discontinuation, until disease progression. Patients who discontinue study treatment for any reason other than disease progression or death will continue to undergo tumor-response evaluations until progressive disease or the initiation of another anti-cancer therapy, whichever occurs first. At the investigator's discretion, scans may be repeated at any time if progressive disease is suspected.

Patients who have demonstrated control of their systemic disease (defined as having received clinical benefit [i.e., a PR, CR, or SD for ≥ 3 months]), but who have developed brain metastases that are treatable with radiation, will be allowed to continue to receive study treatment until they either experience systemic progression of their disease and/or further progression in the brain (based on investigator assessments).

To ensure a valid comparison of tumor data and uniformity in the assessment of tumor response during the study, the following procedures must be implemented at the study site:

- All lesions identified at baseline (target and non-target) are to be reassessed using the same method throughout the course of the study.

- All radiologic data (CT scans, MRI scans, bone scans, etc.) obtained for all patients enrolled at the center should be reviewed by the local radiologist who, together with the investigator, will determine the local assessment of response and progression.

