2.2 SAMPLE SIZE DETERMINATION

Estimates of the number of events required to demonstrate efficacy with regard to PFS are based on the following assumptions:

- Two-sided log-rank test at the 0.05 level of significance
- Eighty-five percent power to detect a hazard ratio for inavolisib plus palbociclib and fulvestrant versus placebo plus palbociclib and fulvestrant of 0.65, corresponding to an improvement of 5.9 months (from 11 to 16.9 months) in median PFS for the treatment arm over the control arm
- Exponential distribution of PFS
- An annual dropout rate of 15%

With these assumptions, 194 PFS events are required to achieve 85% power for the primary analysis. The 320 patients will be enrolled over approximately 43 months and the primary analysis is expected to occur approximately 50 months after the first patient randomized.

The minimal detectable difference for the PFS hazard ratio is 0.754 (i.e., an improvement of 3.6 months (from 11 to 14.6 months) in median PFS for the treatment arm over the control arm).

3. **ANALYSIS SETS**

The participant analysis sets for the purposes of analyses are defined in [Table 3](#).

Table 3 Participant Analysis Sets

Participant Analysis Set	Description
FAS	All randomized participants; participants will be included in the analyses according to the treatment they were assigned.
SAS	All participants exposed to study treatment; participants will be analyzed according to the treatment that they actually received.
PK-evaluable	All randomized participants in the inavolisib arm who have at least one evaluable inavolisib plasma concentration.

FAS = full analysis set; SAS = safety analysis set; PK = pharmacokinetic

4. **STATISTICAL ANALYSES**

This section is a summary of the planned statistical analyses of the most important endpoints, including primary and key secondary endpoints. It also describes the sensitivity analysis related to the primary study estimand and any pre-specified subgroup analyses.

The analyses described in this SAP will supersede those specified in the protocol.

4.1 **GENERAL CONSIDERATIONS**

All efficacy analyses will be performed on the full analysis set population, unless otherwise specified. All safety analyses will be performed in the safety analysis set, unless otherwise specified.

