4.2.1 Definition of Primary Estimand

Following the estimand framework introduced in the ICH-E9 addendum (ICH 2020), the attributes of the estimand built around the primary endpoint are defined as follows:

- **Population:** patients with *PIK3CA*-mutant, hormone receptor (HR)-positive, HER2-negative locally advanced or metastatic breast cancer whose disease progressed during treatment or within 12 months of completing adjuvant endocrine therapy and who have not received prior systemic therapy for locally advanced or metastatic disease, as defined in study protocol (refer to Protocol Section 4.1)
- **Variable:** PFS, defined as the time from randomization to the first occurrence of disease progression as determined by the investigator and according to response evaluation criteria in solid tumors (RECIST) v1.1, or death from any cause (whichever occurs first)
- **Treatment:**
 - Experimental: inavolisib 9-mg tablet taken PO QD on Days 1–28 of each 28-day cycle, palbociclib 125-mg capsule or tablet taken PO QD on Days 1–21 of each 28-day cycle, and fulvestrant 500 mg administered by IM injection on Days 1 and 15 of Cycle 1 and then on Day 1 of each subsequent 28-day cycle
 - Control: placebo tablet taken PO QD on Days 1–28 of each 28-day cycle, palbociclib 125-mg capsule or tablet taken PO QD on Days 1–21 of each 28-day cycle, and fulvestrant 500 mg administered by IM injection on Days 1 and 15 of Cycle 1 and then on Day 1 of each subsequent 28day cycle
- **Intercurrent events and handling strategies:**
 - Start of non-protocol anticancer therapy prior to disease progression
 - Early discontinuation from study treatment for any reason prior to a PFS event
 - Handling ICE: Following treatment policy, the above ICE will be ignored and tumor assessment data collected after the ICE will be included in the primary PFS analysis
- **Population-level summary:** Hazard ratio for PFS

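### The composite PFS analysis in SAP 4.2.4 drops its own event when non-protocol therapy starts after randomization but before (or without) study treatment

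*SAP*

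**What the plan says.** SAP Section 4.2.4 adds two supplementary analyses of investigator-assessed PFS. They differ from the primary analysis in how they treat NPT started before progression.

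- **Hypothetical strategy.** Patients are censored at the last disease assessment before NPT. An exception follows: "If patients start any NPT before starting study treatment, then the data of those patients will be censored at the time of randomization".
- **Composite strategy.** Here "use of any NPT prior to disease progression will be considered as a PFS event (progression) at the time of initiation of NPT". The next sentence is the same exception, identical except for a comma.

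The section's lead-in keeps the population of the primary estimand. The efficacy set in SAP Section 3, Table 3 is "All randomized participants; participants will be included in the analyses according to the treatment they were assigned". In SAP Section 4.2.1 PFS runs from randomization. The primary analysis follows treatment policy, so that "tumor assessment data collected after the ICE will be included in the primary PFS analysis".

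Two exclusions in Protocol Section 4.1.2 limit NPT before randomization: "Any prior systemic therapy for metastatic breast cancer" and "Chemotherapy, radiotherapy, or any other anti-cancer therapy within 2 weeks before randomization".

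**The concern.** A composite strategy treats the intercurrent event as a failure. The exception treats the same event as grounds for removing the patient at time zero whenever it precedes the first dose. Neither document gives a reason, and the near-identical text suggests that the sentence was carried over from the hypothetical bullet, although that is an inference.

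At stake is the coherence of one pre-specified supplementary analysis. That analysis has a particular use here. Protocol Section 4.5.5 says that patients who stop treatment without progression "will continue to undergo tumor-response evaluations until progressive disease or the initiation of another anti-cancer therapy, whichever occurs first". After NPT, the treatment-policy analysis therefore has few scheduled scans to draw on, and the hypothetical analysis must assume that starting NPT is uninformative. The composite analysis avoids both difficulties, but only if it counts the event that it defines.

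**Working it through.** **1. One patient under each rule.** Take a patient who is randomized, starts NPT some days later, and has not been dosed (or never is).

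| Analysis | Handling | Contribution |
|---|---|---|
| Primary, treatment policy | NPT ignored | Later progression or death, if observed |
| Hypothetical | Censored at last assessment before NPT | With no post-baseline scan, censored at randomization; the exception changes nothing |
| Composite, event rule | Event at NPT start | One event at a positive time |
| Composite, with the exception | Censored at randomization | No event, no follow-up |

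The exception has a proper use for NPT before randomization, but the two exclusions quoted above leave little of that beyond eligibility deviations.

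**2. The plan's own figure.** Inputs from SAP Section 2.2: HR 0.65, two-sided alpha 0.05, power 85%. With 1:1 allocation, events = 4(1.960 + 1.036)² / (ln 0.65)² = 35.91 / 0.1856 = 193.5, so 194 as stated. This point does not touch that figure.

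**3. Size by hand.** Under the exception a patient is in effect deleted. Restoring an early event adds (1 − p) to the Cox score for an inavolisib patient and −p for a placebo patient. With equal numbers at risk, p = 0.65/1.65 = 0.394. The simulated standard error of log HR is 0.146, so the information is 1/0.146² = 46.9. The change in HR is roughly 0.65 × (score/information):

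- one inavolisib patient: 0.65 × 0.606/46.9 = +0.0084
- one placebo patient: −0.65 × 0.394/46.9 = −0.0055
- one in each arm: 0.65 × 0.212/46.9 = +0.0029

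**4. Size by simulation.** Inputs from the SAP: 160 patients per arm, accrual over 43 months (taken as uniform), exponential PFS with control median 11 months and HR 0.65, 15% annual dropout, cutoff at 194 events. There were 4,000 trials and the mean cutoff was 48.9 months, against about 50 in the SAP. Assumed: the number affected, and NPT starting 0.25 to 1.0 month after randomization. The fit is an unstratified Cox model with no other NPT use, so the base case is ordinary PFS rather than a full composite. The change is HR with NPT as an event minus HR with censoring at randomization:

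| Affected patients | Change in HR |
|---|---|
| 1 / 2 / 3, inavolisib only | +0.008 / +0.016 / +0.025 |
| 1 / 2 / 3, placebo only | −0.005 / −0.011 / −0.016 |
| 1 in each arm | +0.003 |
| 3 in each arm | +0.008 |

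The largest case moves HR from 0.656 to 0.680. In standard errors this is ln(0.680/0.656)/0.146 = 0.0359/0.146 = 0.25. Timing matters little: for three inavolisib patients the shift is +0.0250 if NPT starts at 0.1 to 0.5 month and +0.0225 at 1 to 3 months. A second simulation with a fixed 50-month cutoff and NPT at day 7 agrees: 0.650 to 0.675 (three inavolisib), 0.646 to 0.630 (three placebo), 0.651 to 0.660 (three in each arm).

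**5. Events that the primary analysis would keep.** With follow-up uniform on 7 to 50 months, event hazard λ and dropout hazard μ = −ln(0.85)/12 = 0.0135, the chance of an observed event is λ/(λ+μ) × [1 − (e^(−7(λ+μ)) − e^(−50(λ+μ)))/(43(λ+μ))].

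- If all later PFS events are seen (λ = 0.0630 placebo, 0.0410 inavolisib): 0.68 and 0.55 per patient. The simulation with cutoff at 194 events gives 1.98/3 = 0.66 and 1.61/3 = 0.54.
- If only deaths are seen (SAP medians of 35 and 50 months, so λ = 0.0198 and 0.0139, same dropout assumed): 0.34 and 0.26.

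The composite bullet with its exception counts 0; its event rule alone counts about 1.

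**The case against.** The strongest reply is that the affected group may be empty. The sentence does not mention timing relative to randomization, and it does not say whether a patient who is never dosed counts as starting NPT before study treatment. If it covers only patients who are dosed later, hardly anyone qualifies: Protocol Section 4.4.3 prohibits other cancer therapy before and during study treatment, and Section 4.6.1 requires discontinuation for concomitant non-protocol systemic therapy. The analysis carries no alpha and sits beside four sensitivity analyses and another supplementary one. The largest shift needs three affected patients, all in one arm of a double-blind trial.

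Most of this stands, and it sets the severity. It does not rescue the sentence, which as worded can reach randomized, undosed patients in an analysis set that includes them.

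Two criticisms of the numbers also stand. First, the model includes no other NPT use. Adding an assumed background NPT hazard of 0.01 to 0.02 per month gives about 209 to 223 events, and the three-patient inavolisib shift falls to 0.23 to 0.22 standard errors. Second, a reader might infer that the primary analysis would observe more than half an event per affected patient. That needs progression after NPT to be observed, whereas scheduled scans stop at NPT, so the deaths-only figures in step 5 may be nearer the truth.

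**Conclusion.** Minor, and wrong as written. For a randomized patient whose NPT starts after randomization and before or without dosing, the composite bullet discards the event that it has just defined. It also discards any later progression or death that the primary analysis would count if observed.

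On an assumed 1 to 3 patients per arm, HR moves by about 0.003 to 0.008 if they are balanced and by at most about 0.025 (0.25 standard errors) if three fall in the inavolisib arm only. These sizes rest on the assumed counts and timing, an unstratified model although the SAP's is stratified, and ordinary PFS with no other NPT use.

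The documents do not support two stronger readings that a reader might infer. One is that the result of the trial is at risk: the primary analysis ignores NPT altogether, and its alpha, the 194-event trigger and the testing hierarchy are unaffected. The other is that the SAP's rule for missing baseline scans in the central-review analysis (Section 4.2.3) is the same error. Counting deaths in patients whose earlier progression could not be read brings its own bias, so that rule is a trade-off.

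**What to change.** In the composite bullet of SAP Section 4.2.4, replace the exception with:

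*NPT started at or after randomization and before progression, whether or not study treatment was started, is a PFS event at NPT initiation; only patients whose NPT started before randomization are censored at randomization.*

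Report by arm how many patients the rule affects. A same-day start at or after randomization then counts as an event, and never-dosed patients are covered explicitly. The sentence in the hypothetical bullet can stay.

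The cost is one sentence and one small count by arm. No new data are needed and no other analysis changes.

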4.2.4.1 Subgroup Analyses for Primary Endpoint(s)

The generalizability of PFS after randomization results when comparing the addition of inavolisib to standard-of-care treatment with palbociclib plus fulvestrant will be investigated as a part of an exploratory analysis by estimating the treatment effect in subgroups based on the following baseline prognostic factors (including stratification factors):

- Age (<65, ≥65)
- Age (<65, ≥65 to <75, ≥75)
- Sex (Male, Female)
- Ethnicity (Hispanic or Latino; Not Hispanic or Latino)
- Race (White, Black or African American, Asian, American Indian or Alaska Native, Native Hawaiian or other Pacific Islander)
- Visceral disease (yes/no)
- Liver (yes/no)
- Number of organs of disease (<3 vs ≥3)
- Region (North America/Western Europe; Asia; Other)
- Endocrine resistance (primary resistance, secondary resistance)
- Menopausal status at randomization (not post-menopausal, post-menopausal)
- ECOG (0, 1)
- Hormone receptor status (ER+/PR+, ER+/PR-, ER-/PR+)
- Prior treatment in the adjuvant/neo-adjuvant setting:
 - aromatase inhibitor only
 - tamoxifen only
 - aromatase inhibitor and tamoxifen

- an endocrine based combination with a CDK4/6 inhibitor
- prior (neo)-adjuvant chemotherapy (Yes/No)

Further prognostic factors may be considered for subgroup analyses as deemed appropriate. Un-stratified analysis results will be presented for subgroup analyses due to the potentially limited number of patients in each subgroup. Summaries of PFS by above subgroups will be provided in forest plots including estimates for HR and 95% CIs from unstratified Cox proportional hazard models.

